The primary efficacy endpoint is the proportion of subjects in the overall population achieving RBC transfusion independence with a duration of ≥ 56 days (8 weeks). Red blood cell transfusions administered during the 56 days immediately preceding and including the date of randomization will be used to establish baseline requirements. Red blood cell transfusions administered during the treatment period will be used in the efficacy analysis. Red blood cell transfusions administered for elective surgery will not be counted towards baseline requirements, efficacy analysis, or progressive disease status.

Secondary efficacy endpoints include OS, HI-P, proportion of subjects in the overall population achieving RBC transfusion independence with duration of ≥ 84 days (12 weeks), duration of RBC transfusion independence, [≥ 84 days (12 weeks) and ≥ 56 days (8 weeks)], time to RBC transfusion independence [≥ 84 days (12 weeks) and ≥ 56 days (8 weeks)], the proportion of subject progressing to AML, time to AML progression, HI-E (IWG 2006 criteria; [Cheson, 2006](#); [Appendix D](#)), duration of RBC transfusion reduction, the proportion of platelet transfusion-dependent subjects at baseline achieving platelet transfusion independence with duration ≥ 56 days (8 weeks), duration of platelet transfusion independence, time to platelet transfusion independence, hematologic response (IWG 2006 criteria; [Cheson, 2006](#); [Appendix D](#)), and the proportion of subjects experiencing clinically significant bleeding events.

Platelet transfusions administered during the 56 days immediately preceding and including the date of randomization will be used to establish baseline requirements. Platelet transfusions administered during the treatment period will be used in the efficacy analysis. Platelet transfusions

administered for elective surgery will not be counted towards baseline requirements, efficacy analysis or progressive disease status.

Overview of Safety Assessments

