Subjects should continue to receive IP for at least 6 cycles of treatment before being assessed for disease status because, based on prior studies with parenteral azacitidine therapy, response to treatment may be significantly delayed ([Silverman, 2006](#)). While on double-blinded treatment, subjects will continue to receive best supportive care, thus the requested 6-month minimum treatment period does not represent an undue risk to subjects. In addition, because overall survival is one of the endpoints, the effect of extended therapy is being evaluated; suspension of therapy at an early time point may blunt any possible extended survival. Crossover between the treatment groups is not allowed so as not to compromise the overall survival endpoint.

The primary endpoint, RBC transfusion independence, is defined as the absence of any RBC transfusion during any consecutive “rolling” 56 days during the treatment period compared with an average transfusion requirement of ≥ 2 units/28 days of RBCs confirmed for a minimum of 56 days immediately preceding and including the date of randomization. Achieving RBC transfusion independence is likely to be a substantial clinical benefit in a patient population with a median overall survival of approximately 14 to 16 months ([Garcia-Manero, 2008a](#); [Cruz, 2010](#); [Yong, 2010](#)).

Analysis of the primary endpoint will be conducted only once after full (100%) information is available for RBC transfusion independence rates (ie, after all subjects have completed 12 months of double-blind treatment or discontinued before reaching 12 months of double-blind treatment). Twelve months was selected as the duration of double-blind treatment based on the same reason mentioned above that a hematologic response to azacitidine treatment may frequently be delayed ([Silverman, 2006](#)).

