6.7 Efficacy

6.7.1 Transfusion Assessment

The type, number of units, reason and date of transfusions are to be collected after the date of randomization and until 28 days after the last dose of IP or until the last study visit, whichever

occurs later. The Hgb value for which any RBC transfusion is given, and the platelet value for which any platelet transfusion is given, must also be recorded on the CRF. Red blood cell and/or platelet transfusions administered for elective surgery will not count toward baseline requirement, efficacy assessment, or progressive disease status.

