10.4 Background and Demographic Characteristics

Demographic and baseline disease characteristics will be summarized by treatment group for the ITT, mITT, and safety populations. Subjects' age, height, weight, body mass index (BMI), and continuous baseline characteristics will be summarized using descriptive statistics (N, mean, SDev, median, minimum, maximum), while age group, gender, race and other categorical variables will be provided using frequency tabulations (count, percent) by treatment group. Summaries of baseline disease characteristics will include WHO MDS diagnosis classification, IPSS risk classification, time since initial MDS diagnosis, ECOG performance status, bone marrow blasts (%), Hgb (g/dL), platelet counts ($10^9/L$), average baseline RBC transfusion requirement

(unit of RBC per 28 days), platelet transfusion status (dependent or independent), and IPSS cytogenetic classification. For laboratory and vital sign measures, the most recent assessment on or prior to the date of randomization will be used for baseline. Baseline transfusion history will include all transfusions up to and including the date of randomization.

Medical history data (coded by the Medical Dictionary for Regulatory Affairs [MedDRA] dictionary) will be summarized using frequency tabulations by treatment group, system organ class and preferred term for the ITT, mITT, and safety populations.

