10.6.1 Primary Efficacy Analysis

The primary efficacy endpoint of RBC transfusion independence is defined as the absence of any RBC transfusion during any consecutive “rolling” 56 days during the treatment period, ie, Day 1 to 56, Day 2 to 57, Day 3 to 58, etc. Subjects with less than 56 days of assessment during the double-blind treatment period will be counted as non-responders. The primary efficacy analysis will be performed on the ITT population and will compare the RBC transfusion independence rates in the two treatment groups. The number and percentage of subjects achieving RBC transfusion independence and corresponding 95% confidence intervals (CI) will be tabulated and presented by treatment group. A stratified Mantel-Haenszel (MH) chi-squared test, stratifying for average baseline RBC transfusion requirement (≤ 4 units^{§§} versus > 4 units of RBC per 28 days), baseline platelet transfusion status (dependent or independent), country of enrollment (ie, Japan versus ROW) and ECOG performance status (0 to 1 versus 2), at a two-sided alpha level of 0.05, will be used to compare the RBC transfusion independence rate between the two treatment groups. The p-value from the stratified MH chi-square test will be the confirmatory p-value for the test of the null hypothesis that the proportion of subjects achieving RBC transfusion independence is equal between the two treatment groups. Summaries will include the difference in proportions between the two treatment groups with corresponding 95% CI and the common odds ratio with corresponding 95% CI. Subject listings with supporting data will be provided.

The analysis of the primary endpoint will be repeated for the mITT population as the supportive analysis. Additionally, the following sensitivity analyses will be conducted:

- In subjects considered baseline transfusion dependent based on transfusions given for a hemoglobin value ≤ 9.0 g/dL for 56 days;
- In subjects considered baseline transfusion dependent based on transfusions given for a hemoglobin value ≤ 9.0 g/dL for 84 days.

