RBC transfusion history must be available for the 56 days immediately preceding and including the date of randomization. Transfusion data should include the type, number of units, reason and date of transfusion. Transfusion data must include the hemoglobin (Hgb) value for which the transfusion was administered. Hgb levels at the time of or within 7 days prior to administration of a RBC transfusion must have been ≤ 10.0 g/dL for the transfusion to be counted towards RBC transfusion-dependent status. Red blood cell transfusions administered when Hgb levels were > 10.0 g/dL will not qualify as a required transfusion for the purpose of providing evidence of RBC transfusion-dependent status. In addition, any RBC transfusion administered for elective surgery will not qualify towards determination of RBC transfusion dependent status at baseline. All RBC transfusion records for the 56 days immediately preceding the date of randomization should be collected, regardless of Hgb levels. RBC transfusion-dependent anemia at baseline is defined for this protocol as documentation of an average transfusion requirement of at least 2 units of RBCs per 28 days during the 56 days immediately preceding the date of randomization. There must also not be any consecutive 28 days within the 56-day period in which no RBC transfusions were administered. Platelet transfusion history, if applicable, must be available for the 56 days immediately preceding and including the date of randomization. Transfusion data must include the platelet value for which the transfusion was administered.

Platelet transfusion-dependence at baseline is defined for this protocol as at least 2 separate transfusion episodes during the 56 days immediately preceding the date of randomization. There must also not be any consecutive 28 days within the 56-day period in which no platelet

transfusion was administered. In addition, any platelet transfusions administered for elective surgery will not qualify towards determination of platelet transfusion dependent status at baseline.

Thrombocytopenia at baseline must be confirmed by two platelet counts that are $\leq 75 \times 10^9/L$ and ≥ 21 days apart. The second confirmatory platelet count must be obtained ≤ 14 days prior to randomization.

Other screening assessments will be also collected according to the protocol.

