8.2. Baseline Disease Characteristics

Baseline disease characteristics includes following variables:

- MDS World Health Organization (WHO) 2008 classification,
- Eastern Cooperative Oncology Group (ECOG) performance status (0 – 1, 2),
- Time since initial diagnosis (defined as the number of months from the date of initial diagnosis to the date of randomization),
- IPSS score classification ([Greenberg, 1997, Appendix C](#)),
- Baseline platelet transfusion status (Dependent, Independent),
- Average baseline RBC transfusion requirements (units per 28 days) and category (≤ 4 units per 28 days, > 4 units per 28 days),
- Bone marrow blasts baseline values and category ($< 5\%$, $\geq 5\%$),
- Hgb (g/dL) values,
- Platelet count ($10^9/L$) values,
- Absolute neutrophil count ($10^9/L$) values,
- White blood cell count ($10^9/L$) values,

- Transferrin saturation baseline values (%) values.

Subjects will be considered platelet transfusion dependent at baseline if they have received ≥ 2 platelet transfusions during the 56 days immediately preceding randomization and had no consecutive 28-day period during which no platelet transfusions were administered.

The average number of units (in 28 days) of baseline RBC transfusions is determined by the following rules:

If the subject was randomized under the original protocol and protocol amendment 1, the average number of units per 28 days = sum of RBC transfusion units during the 84-day interval prior to the randomization date / 84 days * 28 days.

- If the subject was randomized under protocol amendment 2, the average number of units per 28 days = sum of RBC transfusion units during the 56-day interval prior to the randomization date / 56 days * 28 days.
- RBC transfusion and whole blood transfusion during the above specified period will be included. For whole blood transfusion, the number of units collected in the CRF will be used to calculate the RBC transfusions required units.

To eliminate the impact of transfusion, the baseline values for Hgb will be determined by following steps:

Step 1: Apply the “7-day rule” on all Hgb values from the Central lab which are collected on or prior to Cycle 1 Day 1. Use the lowest value among the Hgb values which are collected after >7 days of a RBC/whole blood transfusion or collected on the same of the transfusion as the baseline value.

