10.1. Analysis of Primary Efficacy Endpoint

The primary efficacy endpoint of RBC transfusion independence is defined as the absence of any RBC transfusion during any consecutive "rolling" 56 days within the treatment period. A subject who did not receive any RBC transfusion during a consecutive rolling 56 days (i.e., day 1 to day 56, day 2 to day 57) will be considered as a 56-day RBC transfusion independent responder. Subjects without achieving the response as defined above, subjects with less than 56 days of assessment during the double-blind treatment period, and subjects who had average baseline RBC transfusion units less than 2 units per 28 days (as defined in Section 8.2) will be counted as non-responders.

All RBC transfusion records on or after randomization within the evaluation period will be used to assess the response for each subject. In other words, the days after the end of the evaluation period will not contribute to a rolling period. The end date of the evaluation period is defined as:

- For a subject who discontinues the treatment,

- If the subject doesn't receive a subsequent MDS treatment, use the date of end of treatment visit;
- If the subject receives a subsequent MDS treatment, use the start date of the subsequent MDS treatment – 1 day, or the date of end of treatment visit, whichever is earlier;
- For a subject who is still on-treatment at the time of the database lock for the primary analysis, the subject's latest available assessment date in the database (from AE, vital sign, local and central lab, study drug records, efficacy assessments) will be used.

The 56-day rolling period for the RBS transfusion independent assessment starts on the date of randomization.

Note if the interval between the last RBC transfusion in the evaluation period (if there is at least one RBC transfusion during the evaluation period) and the end date of the evaluation period is less than 56 days, this rolling period, which is less than 56 days, won't be considered as meeting the transfusion independence criteria even though there is no RBC transfusion in it. The day on which the transfusion is received will not contribute to the 56-day without receiving RBC transfusion rolling period.

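### SAP 10.1 leaves the protocol's elective-surgery exclusion out of the primary endpoint, and the transfusion limb of HI-E is defined in three conflicting ways

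*SAP*

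**What the plan says.** **Elective surgery.** The Protocol Summary (Overview of Efficacy Assessments) says: "Red blood cell transfusions administered for elective surgery will not be counted towards baseline requirements, efficacy analysis, or progressive disease status". Protocol 6.7.1 repeats this for RBC and platelets: "transfusions administered for elective surgery will not count toward baseline requirement, efficacy assessment, or progressive disease status". The same section has sites record the reason for each transfusion.

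The protocol's endpoint definitions do not carry the exclusion. Section 10.6.1 reads "The primary efficacy endpoint of RBC transfusion independence is defined as the absence of any RBC transfusion during any consecutive" rolling 56 days, and Section 4.2 uses nearly the same words. Section 10.4 says "Baseline transfusion history will include all transfusions up to and including the date of randomization".

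SAP 10.1 also defines response as no RBC transfusion of any kind in a rolling 56 days, and adds "All RBC transfusion records on or after randomization within the evaluation period will be used to assess the response for each subject". SAP 8.2 computes baseline units with the note "RBC transfusion and whole blood transfusion during the above specified period will be included". For RBC, the SAP mentions elective surgery only in 4.1.1, and only for eligibility-type dependence: "any RBC transfusion administered for elective surgery will not qualify towards determination of RBC transfusion dependent status at baseline".

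**HI-E, transfusion limb.** A response is a reduction of at least 4 units per 8 weeks. The transfusions that count are:

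- Protocol Appendix D, which Protocol 10.6.2.2 makes the definition: those given at Hgb ≤ 9.0 g/dL on treatment.
- SAP Appendix E: those given at ≤ 9.0 g/dL pretreatment.
- SAP Appendix F (18.6.3): those given at ≤ 10.0 g/dL on treatment. It then confirms the reduction through SAP 10.2.11, which has no hemoglobin condition.

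SAP 16 lists the departures from the protocol's statistical section and says there are no others. The HI-E threshold is not on the list.

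**The concern.** The primary endpoint carries the confirmatory test and is the condition for any formal inference on OS. A subject with a single transfusion-free stretch, interrupted only by a transfusion for an operation, is a responder under Protocol 6.7.1 and can be a non-responder under SAP 10.1. For transfusion independence the error goes one way on treatment: it can only remove responders, in either arm. SAP 10.2.3 (84-day independence), 10.2.11 (transfusion reduction) and 10.2.12 (platelets) derive their responses in the manner of 10.1, so they share the gap.

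At baseline, counting surgical units can only raise the average. For subjects who met inclusion criterion 3 it cannot cause failure of the check for at least 2 units per 28 days. It can move a subject from the ≤ 4 to the > 4 units stratum.

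For HI-E, one set of transfusion records can be a response under one passage and not under another, so the derived count depends on which text is followed.

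**Working it through.** **(a) Primary endpoint**

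Inputs (Protocol 10.3, SAP 4.4): 108 per arm; 0.30 vs 0.05 and 0.15 vs 0.05; two-sided alpha 0.05; un-pooled variance.

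*Stated power.* Power = Φ(|p1 − p2|/SE − 1.96), with SE = √{[p1(1−p1) + p2(1−p2)]/108}.

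- 0.30 vs 0.05: SE = √(0.2575/108) = 0.0488; power 0.999 (stated about 99%).
- 0.15 vs 0.05: SE = √(0.175/108) = 0.0403; power 0.700 (stated about 70%).

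Both figures reproduce.

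*How a responder is lost (constructed example).* Transfusions on days 20 and 130, a surgical transfusion on day 75, evaluation ends on day 140. Counting all records, the free runs are 19, 54, 54 and 10 days: non-responder. Excluding the surgical record, days 21 to 129 give 109 free days: responder.

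*Who is exposed.* One surgical date splits a run of L days into two pieces totalling L − 1. If L ≥ 112, one piece has at least 56 days and the response survives. Only subjects whose qualifying runs are all 56 to 111 days long can be lost to a single surgical date.

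*Effect on the test.* Responders at the planning rates: 0.15 × 108 ≈ 16, 0.05 × 108 ≈ 5, 0.30 × 108 ≈ 32. Unstratified Mantel-Haenszel chi-square with equal arms, a active responders and m responders in total: (a − m/2)² / [0.25·m·(216 − m)/215]. Placebo is held at 5.

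| Active responders | Lost from 16 | p |
|---|---|---|
| 16 | 0 | 0.0117 |
| 15 | 1 | 0.0192 |
| 14 | 2 | 0.0310 |
| 13 | 3 | 0.0494 |
| 12 | 4 | 0.0776 |

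Starting from 32, the last two rows are reached after 19 and 20 losses.

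*If both arms lose alike.* Assume 2%, 5% or 10% of responders are lost in each arm. Power at 0.15 vs 0.05 falls from 70.0% to 69.0%, 67.5% or 64.8%. At 0.30 vs 0.05 it stays at 99.7% or above.

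**(b) HI-E transfusion limb**

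Reduction = counted baseline units − counted on-treatment units in one 56-day window; response if ≥ 4. Each hemoglobin filter is applied only to the period its text names. The records are constructed and say nothing about frequency.

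- Set 1: baseline 4 units at 8.5 and 4 at 9.5; on treatment 4 at 9.5.
- Set 2: baseline 8 at 9.5; on treatment 4 at 9.5 and 2 at 10.5.
- Set 3: baseline 6 at 8.5; on treatment 4 at 9.5 and 2 at 8.5.

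| Rule | Set 1 | Set 2 | Set 3 |
|---|---|---|---|
| Protocol App. D | 8 − 0 = 8, yes | 8 − 0 = 8, yes | 6 − 2 = 4, yes |
| SAP App. E | 4 − 4 = 0, no | 0 − 6 = −6, no | 6 − 6 = 0, no |
| SAP App. F | 8 − 4 = 4, yes | 8 − 4 = 4, yes | 6 − 6 = 0, no |
| SAP 10.2.11 | 8 − 4 = 4, yes | 8 − 6 = 2, no | 6 − 6 = 0, no |

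Set 1 separates Appendix F from Appendix E. Set 2 separates Appendix F from its own check. Set 3 separates the protocol's rule from the SAP's derivation.

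**The case against.** On the primary endpoint, the SAP sentence about all records is followed at once by an explanation of which days fall inside the evaluation period. It reads as a time window, not as a rule on why a transfusion was given. A specific protocol exclusion for efficacy would ordinarily qualify a general definition, and nothing in the SAP revokes it. Protocol 10.4 can be read as describing history, and the SAP 8.2 note as describing product type. These readings are fair, and a careful programmer might reach them. But the SAP states no on-treatment exception anywhere, its own definition is unqualified, and it repeats the exclusion only for baseline dependence. Protocol 10.6.1 gives the programmer no help.

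The p-value table is a one-sided worst case: 4 of 16 active responders (25%) lost and no placebo responder. It is unstratified, whereas the confirmatory test is stratified. Nothing in the documents suggests an arm difference in elective surgery, and runs of 112 days or more are safe from one surgical date. All of that stands and limits the likely size.

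On HI-E, SAP 10.2.10 names Appendix F as the derivation, so Appendix E may be only a reference table. Its result in Set 1 also depends on leaving on-treatment units unfiltered: filtering both periods at 9.0 gives 4 − 0 = 4. If confirmation means both conditions must hold, Set 2 has one answer within Appendix F. These points weaken Sets 1 and 2 but not Set 3. There the protocol's rule gives 4 whether or not baseline is filtered, while Appendix F and 10.2.11 both give 0. HI-E is also summarized separately from the investigator's CRF assessment, which this does not touch.

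**Conclusion.** The concern holds on both parts. The protocol excludes elective-surgery transfusions from efficacy in two places. SAP 10.1, followed literally, counts them, and the protocol's own endpoint sections do not settle the matter. The effect is 0.9 percentage points (1/108 = 0.93%) per reclassified subject. The documents give no frequency of elective-surgery transfusion, so the total cannot be estimated. It could decide the test only if the observed effect were near the lower planning scenario and the losses fell mainly in the active arm; near 0.30 vs 0.05 it is unlikely to matter.

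For HI-E, the three hemoglobin rules differ in threshold and in the period filtered, and Appendix F departs from the protocol's definition without being declared in SAP 16. This affects a secondary endpoint outside alpha control and leaves the confirmatory test untouched. This review does not say which threshold is correct.

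**What to change.** In SAP 8.2 and 10.1, and in 10.2.3, 10.2.11 and 10.2.12, which follow 10.1, state that transfusions whose recorded reason is elective surgery are excluded. Add the same exception to Protocol 10.6.1.

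For HI-E, state one transfusion-counting rule giving the threshold and the period, preferably counting baseline and on-treatment units on the same basis. Bring Protocol Appendix D, SAP Appendices E and F, and Appendix F's confirming check into line with it. Change the check in Appendix F rather than the hemoglobin-free definition of transfusion reduction in SAP 10.2.11, which matches Protocol 10.6.2.2. List any remaining departure in SAP 16.

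The primary clinical study report was final by 04-Feb-2020, so new wording cannot alter the reported analysis. Report as a post hoc consistency check how many RBC transfusions in the baseline and evaluation periods were for elective surgery, by arm, and whether any subject's primary or HI-E responder status changes. If none does, one sentence closes the point. The cost is wording plus one re-derivation from data already collected (transfusion reason and pre-transfusion hemoglobin).
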